8.4.2 Definition of Serious Adverse Events (SAE)

A serious adverse event (SAE) is defined by federal regulation as any AE occurring at any dose that results in any of the following outcomes: death, life-threatening AE, hospitalization or prolongation of existing hospitalization, a persistent or significant disability/incapacity, or a congenital anomaly/birth defect.

Important medical events that may not result in death, be life threatening, or require hospitalization may be considered an SAE when, based upon appropriate medical judgment, they may jeopardize the subject and may require medical or surgical intervention to prevent one of the outcomes listed in this definition. Examples of such medical events include allergic

bronchospasm requiring intensive treatment in an emergency room or at home, blood dyscrasias or convulsions that do not result in subject hospitalization, or the development of drug dependency or drug abuse.

8.4.2.1 Overdose

Not applicable.

8.4.3 Classification of AE

8.4.3.1 Severity of Event

The severity of all AE, will be assessed by the Investigator and should be classified as mild, moderate, or severe. Severity will be graded according to the following definitions:

Mild: The subject experiences awareness of symptoms but these are easily tolerated or managed without specific treatment.

Moderate: The subject experiences discomfort enough to cause interference with usual activity, and/or the condition requires specific treatment.

Severe: The subject is incapacitated with inability to work or do usual activity, and/or the event requires significant treatment measures.

8.4.3.2 Relationship to Study Intervention

The relationship of the event to the investigational product should be determined by the Principal Investigator according to the following criteria:

Not Related: The event is most likely produced by other factors such as the subject's clinical condition, intercurrent illness, or concomitant drugs, and does not follow a known response pattern to the trial product which makes a causal relationship unlikely.

Related: The event follows a temporal relationship or known response pattern to the trial product, and cannot be explained by other factors such as the subject's clinical condition, intercurrent illness, or concomitant drugs.

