2.3 Risk/Benefit Assessment

2.3.1 Known Potential Risks

The major risk associated with use of human tissue, even as a temporary, non-engrafting therapeutic, is the transmission of infectious agents. This risk is minimized through careful donor screening, Good Tissue Practices, and aseptic current Good Manufacturing Practices (cGMP) processing. Decellularization removes any risk of potential graft vs. host reactions. A review of the literature indicates that various cell and tissue based products tested as therapeutics for non-healing wounds show no differences in adverse event profile compared with SC alone. Experience with a 361 HCT/P version of TTAX01 (NEOX CORD) in treating DFU indicated that weekly application to large wounds may have been associated with a slightly higher rate of local tissue infection. This issue was not seen in Phase 2 testing at the lower frequency of every 4 weeks. Phlebotomy is performed twice, at baseline and end of study, which carries a minor risk of discomfort and possible hematoma. There have been no reported cases of infectious agent transmission in more than 53,000 distributed units of

NEOX®/CLARIX® 100 (trade name for amniotic membrane products) or NEOX®/CLARIX® CORD 1K® (trade name for umbilical cord products), nor have any remarkable adverse events or serious adverse events been reported related to these products. The protocol itself carries a small risk of delaying healing by virtue of excluding a range of alternative therapies, however, none of these is of proven benefit in healing the high grade ulcers under study.

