8.1.4 Treatment Period (Visits 2– 16; 7 ± 2 days)

[Purpose]: To monitor safety and wound healing, adjust antibiotic regimens, and administer treatment. At each visit of Visits 2 through 16, the listed procedures will be performed for the subject based upon status of the wound.

If the subject will discontinue from TTAX01 treatment at any of these visits, the subject should continue with the scheduled visits through the end of the study in order to observe wound status and general safety. If the subject will discontinue from the trial (drop-out), move immediately to the End of Study Visit (Visit 29) and complete all of the procedures listed.

Beginning at Visit 9 (Day 57), if the wound is not \geq 50% reduced in wound area versus the post debridement measurement obtained at the Initial Procedure Visit prior to randomization, the Investigator may begin to utilize adjunctive therapies as explained in Section 6.5.

If at any Treatment Visit the index ulcer is observed to be closed, perform the following procedures:

- Assess adverse events
- Review concomitant medications
- Assess subject compliance regarding off-loading since the last visit
- Obtain photographs of the closed ulcer using the electronic wound imaging and measuring device
- Observe the wound if it is fully epithelialized with no drainage or need for a dressing, record it as closed.

The next visit scheduled will serve as the first consecutive confirmation visit in 14 ± 2 days and will begin the confirmation of closure procedures (refer to Section 8.1.9).

If the wound remains open, conduct the following procedures:

- Assess adverse events
- Review concomitant medications. These will be recorded in the subject's source document, but should only be recorded in the eCRF for the following:
 - All current and past treatments for the index ulcer only
 - Concomitant medications used to treat the index ulcer (e.g., systemic antibiotics for an index ulcer infection) and the peri-ulcer area (such as treatment for erythema, irritation, itching), together with the indication for the medication
 - Concomitant medications used to treat all SAE, and all AE considered "RELATED" to the product will be recorded in the appropriate eCRF.
- Assess subject compliance regarding off-loading since the last visit
- Assess the foot and lower extremity, then assess the index ulcer after removal of the dressing (but do not remove residual TTAX01 in the treatment group).

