8.4.3.3 Expectedness

As with the use of any human tissue, the possibility of infectious agent transmission cannot be completely eliminated although all screening and microbial testing results were satisfactory for the tissue and tissue donor. Possible significant adverse events include microbial infection and transmission of viral disease.

Expected adverse events non-related to the product are those post-surgical conditions consistent with any dermal debridement and excoriation of an ulcer. Potential adverse events for all research subjects in this trial intrinsic to the nature of DFUs: bleeding, hematoma, cellulitis, pain, deteriorating ulcer exudation, erythema, edema, infections including deep tissue infections (osteomyelitis), and occurrence of new ulcers.

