8.4.6 Serious Adverse Event Reporting

In the event of any SAE reported or observed during the trial, whether or not attributable to the trial product, the Investigator, or designee, shall report the event to the medical monitor within 24 hours being made aware of the event. An initial report should be made with the understanding that it may be lacking in details.

A Serious Adverse Event Form must be completed for all serious adverse events and submitted within 24 hours of the Investigator's knowledge of the event and to the Institutional Review Board/Independent Ethics Committee, according to their reporting requirements. When new significant information is obtained as well as when the outcome of an event is known, the Investigator must provide this information as soon as it becomes available. Depending on the nature of the adverse event, copies of the subject's medical records as well as results of any

relevant laboratory tests performed maybe required to be submitted. If the subject was hospitalized, a copy of the discharge summary should be forwarded as soon as it becomes available. In certain cases, a letter from the Investigator that summarizes the events related to the case may be required.

Serious adverse events must be reported using the eCRF system (preferred), or via telephone or email, to the following representative within 24 hours of the Investigator's knowledge of the event:

SAE reports shall be entered into the eCRF and hospital records will be submitted to:

[name]

[contact]

E-mail: [contact]

The study Sponsor will be responsible for notifying the Food and Drug Administration (FDA) of any unexpected fatal or life-threatening suspected adverse reaction as soon as possible, but in no case later than 7 calendar days after the Sponsor's initial receipt of the information. In addition, the Sponsor must notify FDA and all participating Investigators in an Investigational New Drug (IND) safety report of potential serious risks, from clinical trials or any other source, as soon as possible, but in no case later than 15 calendar days after the Sponsor determines that the information qualifies for reporting.

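### The two causality categories in Section 8.4.3.2 are not exhaustive: an event with another possible cause can never be Related, and many such events fit neither category

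*Protocol*

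**What the plan says.** Section 8.4.3.2 of the protocol asks the Principal Investigator to place each event in one of two categories.

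- **Related**: "The event follows a temporal relationship or known response pattern to the trial product, and cannot be explained by other factors". The examples of other factors that follow are the subject's clinical condition, intercurrent illness and concomitant drugs.
- **Not Related**, first condition: "The event is most likely produced by other factors such as the subject's clinical condition, intercurrent illness, or concomitant drugs". The second condition, joined by 'and', is that the event "does not follow a known response pattern to the trial product which makes a causal relationship unlikely".

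Section 8.4.3.3 (Expectedness) then lists events that the disease itself produces in both arms: "Potential adverse events for all research subjects in this trial intrinsic to the nature of DFUs: bleeding, hematoma, cellulitis, pain". The list goes on to exudation, erythema, edema, and "infections including deep tissue infections (osteomyelitis), and occurrence of new ulcers". The paragraph before it names microbial infection among the possible significant events of human tissue.

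The relationship label is used in the AE presentation by System Organ Class and preferred term (9.4.4). It is also used in the rule that two reports of the same event, if serious, unexpected and related, prompt a safety review (10.1.2, 10.1.6). Section 8.4.6 uses a different term for the sponsor's expedited reports to FDA: "any unexpected fatal or life-threatening suspected adverse reaction as soon as possible".

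**The concern.** A two-level causality variable works only if the levels are complements. Here each level carries its own pair of conditions, so an event can fail both.

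The exclusion clause in Related is also absolute. It does not ask whether the product may have contributed. It asks whether anything else could explain the event. In subjects with a deep, infected diabetic foot ulcer, the clinical condition can explain most local events, and Section 8.4.3.3 says so. For those events the label is settled by the definition before the investigator looks at the evidence.

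At stake is the meaning of a safety variable that the protocol reports and acts on. Sites will have to improvise a code for events with no category. They will do so knowing the arm, because site staff are not blinded (6.3).

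**Working it through.** The plan gives no figure to reproduce, and no sample size or power calculation is involved. The check is a full enumeration of the two definitions.

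**Inputs (Section 8.4.3.2)**

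- Temporal link: no or yes.
- Known response pattern: no or yes.
- Other cause: none; possible but not most likely; most likely.

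Combinations: 2 × 2 × 3 = 12.

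**Rules as written**

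- Related = (temporal link OR known pattern) AND no other cause can explain the event.
- Not Related = other cause most likely AND no known pattern. There is no temporal condition.

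| Temporal link | Known pattern | No other cause | Other cause possible, not most likely | Other cause most likely |
|---|---|---|---|---|
| No | No | neither | neither | Not Related |
| No | Yes | Related | neither | neither |
| Yes | No | Related | neither | Not Related |
| Yes | Yes | Related | neither | neither |

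**Counts**

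- All combinations: 3 Related + 2 Not Related + 7 neither + 0 both = 12.
- Some other cause present (last two columns, 8 combinations): 0 Related, 2 Not Related, 6 neither.
- Temporal link and another cause (4 combinations): 0 Related, 1 Not Related, 3 neither.

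These are logical cells, not frequencies. They show where the rule gives no answer, not how often that will happen.

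**A more lenient reading.** Suppose the exclusion clause in Related is read as barring only a most likely other cause. Related then covers 3 × 2 = 6 cells and Not Related still covers 2, so 12 − 8 = 4 cells remain without a category. Two of the four are events that follow a known response pattern and also have a most likely other cause. The gap narrows but does not close.

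**Applied to a local infection after an application.** Section 8.4.3.3 lists infection as intrinsic to the disease, so another explanation is always available and Related is barred. The same section lists microbial infection as a possible event of the tissue product. If that makes infection a known response pattern, Not Related is barred too, and the event has no code. If it does not, the event is Not Related only where the other cause is judged most likely.

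**The case against.** The strongest reply is that safety inference in this trial does not rest on attribution, and most of that reply stands.

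- The trial is randomised against standard care, and the safety endpoint is the proportion of subjects with AEs by group (Section 3). An excess of infections would appear there whatever label each event carries.
- AEs are documented regardless of relationship (8.4.4, 8.4.5), and SAEs go to the medical monitor within 24 hours whether or not attributable (8.4.6).
- Section 8.1.4 limits eCRF recording of treatment for non-serious AEs to those considered related. A separate item in the same list, however, captures medications for the index ulcer and the peri-ulcer area without that condition. Treatment of local events is therefore largely recorded anyway.
- The two-event review also requires the event to be unexpected. Infection, cellulitis and osteomyelitis are listed under Expectedness and would not ordinarily trigger it under any causality wording.
- Nothing ties the sponsor's FDA reporting in 8.4.6 to the investigator's label in 8.4.3.2.

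A reader might infer several stronger points that the documents do not support.

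- *Every event with both a temporal link and another possible cause is uncodable.* Not Related has no temporal condition. A temporally linked event whose other cause is most likely, and which shows no known pattern, is validly Not Related.
- *No local event could ever be Related.* Section 7.2 foresees a product-related allergic skin reaction, which is not on the list of disease-intrinsic events and could qualify.
- *Section 2.3.1 establishes infection as a known response pattern.* It says that "weekly application to large wounds may have been associated with a slightly higher rate of local tissue infection" and then adds that this was not seen in Phase 2 at four-week intervals. The case for infection as a product event rests on 8.4.3.3 and is arguable.
- *Phase 2 demonstrates misattribution.* Section 2.2 reports two of 32 subjects with recurrent or persistent osteomyelitis requiring minor amputation, and no AE attributed to TTAX01. The protocol does not give the Phase 2 causality definition, and correct judgement would give the same result. Scaling those two events to this trial would project disease events, not miscoded ones.

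**Conclusion.** The concern holds as a defect of definition with limited reach. As written, the rule leaves 7 of 12 logical combinations without a category. It bars from Related any event that another factor can explain, which covers most local events in this population because of the protocol's own list in 8.4.3.3.

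Two uses of the label are affected. The tables by relationship in 9.4.4 would report a variable that is partly fixed by wording and partly improvised at sites. The two-event review in 10.1.2 and 10.1.6 could miss serious events that are on no expected list, because comorbid patients nearly always offer another explanation. AE and SAE capture, the comparison between arms and the recording of local wound medications are unaffected.

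The conclusion assumes that the two conditions in each definition are cumulative, as the word 'and' in each indicates. That most local events are barred is a judgement from the list in 8.4.3.3, and the documents give no frequency. How investigators would code the uncategorised events is unknown. A drift towards Not Related is plausible but not shown. The wording should be corrected, but the trial's main safety comparison does not depend on it.

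**What to change.** Replace the two definitions in Section 8.4.3.2 with an exhaustive pair:

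- **Related**: there is a reasonable possibility, from timing, pattern or biological plausibility, that the product contributed to the event, even if the underlying condition or other factors may also have contributed.
- **Not Related**: there is no such reasonable possibility.

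Refer to this one definition wherever the protocol relies on relatedness: the visit procedures that condition eCRF recording on it, 7.2, 9.4.4, 10.1.2 and 10.1.6. State in 8.4.6 how it relates to the term used there for suspected reactions. Listing an event as intrinsic to the disease in 8.4.3.3 should bear on expectedness only and should not settle causality.

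The cost is two sentences in the protocol, the cross-references and the matching text in the eCRF completion guidelines. No trial procedure or sample size changes. The downside is that somewhat more AEs will be labelled related, so the relationship tables will look slightly less favourable to the product.

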8.4.3.3 Expectedness

As with the use of any human tissue, the possibility of infectious agent transmission cannot be completely eliminated although all screening and microbial testing results were satisfactory for the tissue and tissue donor. Possible significant adverse events include microbial infection and transmission of viral disease.

Expected adverse events non-related to the product are those post-surgical conditions consistent with any dermal debridement and excoriation of an ulcer. Potential adverse events for all research subjects in this trial intrinsic to the nature of DFUs: bleeding, hematoma, cellulitis, pain, deteriorating ulcer exudation, erythema, edema, infections including deep tissue infections (osteomyelitis), and occurrence of new ulcers.

8.4.4 Time Period and Frequency for Event Assessment and Follow-Up

The occurrence of an AE or SAE may come to the attention of study personnel during study visits and interviews of a study participant presenting for medical care, or upon review by a study monitor.

All AEs including local and systemic reactions not meeting the criteria for SAEs will be captured on the appropriate case report form (CRF). Information to be collected includes event description, date of onset, clinician's assessment of severity, relationship to study product (assessed only by those with the training and authority to make a diagnosis) confirmed by the Principal Investigator, and date of resolution/stabilization of the event. All AEs occurring while on study must be documented appropriately regardless of relationship.

Any medical condition that is present at the time that the participant is screened will be considered as baseline medical history and not reported as an AE. However, if the study participant's condition deteriorates at any time during the study, it will be recorded as an AE.

Changes in the severity of an AE will be documented to allow an assessment of the duration of the event at each level of severity to be performed. AEs characterized as intermittent require documentation of onset and duration of each episode.

The Investigator will record all reportable events with start dates occurring any time after informed consent is obtained until the final study visit. At each study visit, the Investigator will inquire about the occurrence of AE/SAEs since the last visit. Event outcome at resolution or at time of last follow up will be recorded as "event resolved", "resolved with sequelae", "ongoing at discontinuation", or "death".

8.4.5 Adverse Event Reporting

Disease Related Events expected in this population (angina, neuropathy, nephropathy, urinary tract infection, erectile dysfunction, retinopathy, hypoglycemic events) may be reported by the Investigator if they differ in nature or frequency from what is expected, or if they appear to have a causal relationship to the test article. All adverse events must be reported in the subject's source documents, and recorded on an Adverse Event Case Report Form regardless of whether or not they are considered to be related to the test article.

8.4.6 Serious Adverse Event Reporting

In the event of any SAE reported or observed during the trial, whether or not attributable to the trial product, the Investigator, or designee, shall report the event to the medical monitor within 24 hours being made aware of the event. An initial report should be made with the understanding that it may be lacking in details.

A Serious Adverse Event Form must be completed for all serious adverse events and submitted within 24 hours of the Investigator's knowledge of the event and to the Institutional Review Board/Independent Ethics Committee, according to their reporting requirements. When new significant information is obtained as well as when the outcome of an event is known, the Investigator must provide this information as soon as it becomes available. Depending on the nature of the adverse event, copies of the subject's medical records as well as results of any

relevant laboratory tests performed maybe required to be submitted. If the subject was hospitalized, a copy of the discharge summary should be forwarded as soon as it becomes available. In certain cases, a letter from the Investigator that summarizes the events related to the case may be required.

Serious adverse events must be reported using the eCRF system (preferred), or via telephone or email, to the following representative within 24 hours of the Investigator's knowledge of the event:

SAE reports shall be entered into the eCRF and hospital records will be submitted to:

[name]

[contact]

E-mail: [contact]

The study Sponsor will be responsible for notifying the Food and Drug Administration (FDA) of any unexpected fatal or life-threatening suspected adverse reaction as soon as possible, but in no case later than 7 calendar days after the Sponsor's initial receipt of the information. In addition, the Sponsor must notify FDA and all participating Investigators in an Investigational New Drug (IND) safety report of potential serious risks, from clinical trials or any other source, as soon as possible, but in no case later than 15 calendar days after the Sponsor determines that the information qualifies for reporting.

